2.2. Preliminary Data

2.2.a. Summary of Work Done: Over the last decade, our group has completed four studies, with

translational and clinical components, demonstrating that yoga interventions are associated with increased thalamic GABA, increased RSA, improved mood, and decreased anxiety. These studies included experienced yoga practitioners, healthy controls, yoga naïve healthy controls, subjects with MDD and low back pain, subjects with MDD and PTSD, and subjects with MDD.(9, 53, 54) Previous studies conducted in civilians were supported by federally funded grants (R21, R01, K03), and resulted in peer reviewed publications, and manuscripts under review and in preparation.

2.2.b. Study 1 (54), Streeter et al 2007⁷, a cross-sectional study, compared changes in GABA levels using magnetic resonance spectroscopy (MRS) in experienced yoga practitioners and healthy controls with no yoga experience at baseline (Scan 1), followed by 60-minutes of hatha yoga practice in yoga practitioners or reading magazines in healthy controls. This was immediately followed by Scan 2. GABA-to-Creatine ratios (GABA/Cr), measured in a 2-cm axial brain slab, showed 27% increase in GABA/Cr in yoga practitioners after the yoga session, but no significant change in healthy controls ($t = -2.99$, $df = 7.87$, $p = 0.018$). This was the first study to document a significant increase in GABA associated with a yoga intervention.

2.2.c. Study 2 (53), Streeter et al 2010 addressed the possibility that increased GABA/Cr in Study 1 could be due to exercise. In a longitudinal RCT, eligible subjects who were yoga naïve, with no Axis 1 disorders, no use of medications known to influence GABA receptors, and no current yoga or mind-body practices received a baseline scan (Scan 1). Subjects were then randomized to a 12-week Iyengar yoga intervention or a group walking intervention that was matched to the yoga intervention for (1) Metabolic Equivalents (METS) by walking 2.5 miles an hour on a flat surface, (2) interaction with research staff and (3) group effect.(55) After the 12-week intervention, subjects underwent Scan 2, immediately followed by a 60-minute yoga or walking intervention, depending on group assignment, prior to Scan 3.

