for certified yoga instructors with Iyengar training who have at least 5 years teaching experience. Instruction in coherent breathing is necessary because the positive effects on sympatho-vagal balance depend not only on the respiratory rate, but also on degree of effort, depth, and muscle relaxation while breathing. Without proper instruction, some inhale too rapidly, overfill their lungs, exhale too forcefully, overuse abdominal muscles, or breathe paradoxically (contracting abdominal muscles while inhaling). Any of these errors could increase sympathetic activation, interfere with parasympathetic activation or even cause hyperventilation. (16) Instructors are needed to observe subject breathing and to monitor and provide corrective feedback.

The COVID-19 pandemic has resulted in all of the yoga instructors providing yoga classes virtually. In order to support social distancing the yoga interventions will be provided virtually through a platform approved by the ISSO officer, such as VA Video Connect. The yoga instructors will teach all yoga interventions virtually. The subjects will be required to attend the randomization, and weeks 4, 8, and 12 interventions at the VABHCS so that equipment can be provided or collect and pre and post intervention data can be collected.

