3.3.2.12. Walking Intervention: The walking intervention was developed and used in Study 2. The literature documents the benefit of physical activity in the treatment of depression, such that a walking group can be considered an active control.(47) For the in-person walking intervention, subjects walk in an indoor circuit with a defined length such that the number of circuits required for a rate of 2.5 miles an hour rate are completed in 60- minutes. Subjects are monitored so that they complete 25% of the required circuits every 15-minutes. The time for the group walking intervention is 60-minutes per group session and the homework is for 15-minutes three times a week, beyond typical walking. The walking group and homework are designed to match the physical activity of the yoga group (i.e., time spent doing yoga postures), not the length of yoga sessions, this results in the walking intervention taking less time than that of the yoga group, with the extra time in the yoga group due to the breathing exercise that does not include group interactions or physical exertion. Study staff will be trained to monitor the intervention and direct subjects to ensure the correct number of laps are completed.

In order for the interventions to be as balanced as possible, the subjects assigned to the interventions will need to come to the VABHCS the same number of times as the subject assigned to the yoga intervention. For the virtual walking sessions, subjects will check in with research staff at the beginning and end of each session by video or telephone. Virtual walking sessions will also include walking at 2.5 miles an hour on a flat surface. During the screening process, subjects will be evaluated for stride length,such that the number of steps to equal 2.5 miles will be calculated. At the randomization session, subjects will be instructed on how to use the pedometer. Subjects will wear a pedometer for each walking session, both in-person and at home, the number of steps for each session will be recorded four times during the intervention and at the end of the homework to document the distance walked. Subjects can provide documentation of the number of steps by photographing the pedometer and sending an email or text or by reporting to the walking intervention monitor during the session.

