4.6.1.16. Confidentiality Risk Protection: Information is kept in separate databases. 1) To ensure confidentiality, all information on clinical report forms (CRFs) or placed directly into REDCap will be marked with subject IDs so that it cannot be associated with any individual. 2) A master list, with individual names and their subject IDs, will be kept in a locked file cabinet or password-protected computer file that can be accessed only by research staff. 3) Identifiable information is kept in a third database. The information gathered will only be used for scientific, educational, or instructional purposes. Exceptions to this rule will be made for representatives of the FDA, other U.S. government agencies, and other mandatory bodies as required by law. Because of the sensitive nature of the questions surrounding the use of illegal substances, a Certificate of Confidentiality will be obtained. While subjects are instructed that the groups are confidential, by the nature of conducting the classes in a group the confidentiality of what is said in the group cannot be guaranteed. For this reason, subjects are instructed to monitor what they say in the group settings. Subjects are informed that they can ask to speak to a staff member in private.

4.6.1.17. COVID-19 Risk Protection: In addition to the already approved safety measures for when
Page 37 of 46

the participants are at the VABHCS additional measures to increase social distancing have been added. The change of the in-person interventions to virtual interventions except for the randomization, and weeks 4, 8, and 12 evaluation is a change that could affect the scientific integrity of the study. As no subject had started the interventions prior to the shutdown of all non-essential research in March 2020, all subjects will have the same experience of virtual interventions. The Veterans Administration Central Office (VACO) Project Manager has given tacit approval to this change, provided it is IRB approved and the documents reflecting VACO approval of the changes are filed by the VABHCS ACOS with VACO. The changes to the intervention to make them virtual have been listed in the protocol. The video connections will be made with VA Video Connect or another platform approved by the VABHCS Information System Security Officer (ISSO).

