4.6.3. Potential Benefits

4.6.3.1. General Benefits: All subjects will have the benefit of an evaluation of their depressive symptoms by clinical staff. Subjects, who have a MRI scan at the McLean Hospital, will have the advantage of having the anatomic study read as part of the safety protocol.

4.6.3.2. Benefits of the Yoga Intervention: The yoga intervention in this protocol includes yoga postures and yoga breathing. Both practices have been shown to have health benefits in controlled trials of normal subjects and clinical populations. In addition to the benefit of physical activity, the yoga intervention includes exercises for flexibility, strength and balance. Yoga practices have been associated with stress reduction, weight reduction, improved sleep, and decreased blood pressure to name a few of it's health benefits. Yoga practices have been shown to decrease symptoms in disorders with low GABA activity such as depression, post traumatic stress disorder (PTSD), epilepsy and chronic pain. There have been controlled studies showing yoga-based interventions to be effective in treating depression ranging from mild depression symptoms to major depressive disorder. The benefits to the subjects participating in this study include the both the general health benefits of yoga and the potential to treat the depressive symptoms.

4.6.3.3. Benefits of the Walking Intervention: There is an extensive literature that exercise improves mood such that the walking intervention is an active control. The walking intervention includes the benefit of regular exercise.

4.6.3.4. Additional Benefits: Social interaction with the research staff and the group members in a population that can be socially isolated is a benefit. Additional benefits include an evaluation by a physician who will discuss treatment options if the subject does not participate in the study. Subjects are closely monitored during the study for increasing symptoms of depression.

IMPORTANCE OF KNOWLEDGE TO BE GAINED

4.6.3.5. Understanding the Relationship Between Yoga Practices, Parasympathetic Tone and Mood:

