A Randomized Control Trial Treating Depression With Yoga and Coherent Breathing Versus Walking in Veterans

NCT03489122

Document Date: 3-20-2017

D.17. Data Management and Analysis Plan: The Data Coordinating Center at the Boston University School of Public Health will provide data management, including the development and maintenance of a REDCap database and the creation of a final database that will be sent to [name] for statistical analysis, using SPSS 23.0. Descriptive statistics will be generated for baseline data and distributions between the yoga intervention and walking intervention will be compared using two-sample t-tests and chi-square or Fisher's exact tests to assess effectiveness of randomization. Descriptive statistics include means and standard deviations for continuous variables and group sizes and proportions for categorical variables. All analyses will be performed at the $\alpha = 0.05$ level of significance. Should groups have unequal distributions at baseline, relevant variables will be incorporated in subsequent linear models that will be used to examine intervention efficacy. In order to address the study aims of assessing the relative longitudinal change in dependent variables between yoga intervention and walking intervention groups over time, data will be collected at four time points, pre-randomization, and at weeks 4, 8, and 12. Mixed linear model analyses will be performed focusing on the group x time interaction for the primary effects to be statistically modeled. These analyses will allow for inclusion of data at differing numbers of time points per subject if needed. We will examine different within-subject correlation structures for our interaction model and determine the optimal structure by comparing Akaike information criteria (AIC) values. The correlation structure that yields the lowest AIC will be adopted. Subjects who change antidepressant medications during the study will be included in intent to treat analysis, but will be co-varied for medication changes. Potential cohort effects will be statistically addressed by controlling for group profiles, including group size, breakdown by sex of attendees, instructor, group parameters such as individual or group sessions, and group cohesion/overlap.

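### In the virtual format yoga is a taught class while walkers must only check in at each end, so staff and group contact are probably unequal between arms, and covariate adjustment cannot repair this.

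*Protocol*

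**What the plan says.** **Yoga.** Protocol 3.3.2.11 states: "The yoga instructors will teach all yoga interventions virtually". It also says instructors are needed to watch participants' breathing and correct it. Live teaching is therefore an inference, but a well-supported one.

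**Walking.** In Protocol 3.3.2.12, virtual walkers are covered by the rule that "subjects will check in with research staff at the beginning and end of each session by video or telephone". In addition, "the number of steps for each session will be recorded four times during the intervention". Walkers may document steps "by reporting to the walking intervention monitor during the session", or instead send a photograph of the pedometer by email or text. In person, walkers use an indoor circuit in a 60-minute group session, and their laps are checked every 15 minutes.

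**Group slots.** Protocol 3.3.2.12.1 offers four group sessions a week in each arm, held at the same times. It extends fidelity checks of instructors and walking monitors to virtual delivery. It does not say whether virtual walking takes place as a shared session.

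**Matching.** Protocol 2.2.c says the Study 2 walking control was matched on METs and on "2) interaction with research staff and (3) group effect". Section 3.3.2.12 takes over that control. Its only balancing provision for the virtual format is an equal number of site visits. Section 4.6.3.4 states: "Social interaction with the research staff and the group members in a population that can be socially isolated is a benefit".

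**Acknowledgement.** Protocol 4.6.1.17 concedes that going virtual could affect scientific integrity. It answers that, because nobody had started before the March 2020 shutdown, "all subjects will have the same experience of virtual interventions".

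**Analysis.** Protocol 3.5.1 and SAP D.17 plan to handle cohort effects by controlling for group size, sex mix, "instructor, group parameters such as individual or group sessions, and group cohesion/overlap". Neither lists contact time or mode of contact.

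**The concern.** The walking arm is meant to isolate what yoga adds beyond activity, attention and company. Section 3.3.2.12 defends the shorter walking session on the ground that the extra yoga time is breathing practice without group interaction. That defence relies on group interaction being otherwise comparable. In the virtual format the text keeps a taught class in one arm and requires only brief check-ins in the other.

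Because no one had started before the shutdown, this applies to every participant. Depression and mood scores could respond to contact alone, which the protocol itself calls a benefit. A yoga advantage under Hypothesis I would then not show that postures and breathing produced it. The adjustment list in D.17 dates from 2017, before virtual delivery. It might look like a safeguard, but it cannot serve as one.

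**Working it through.** The plan gives no figure for contact, so there is none to reproduce. Three checks follow.

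**1. Contact per arm**

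Inputs from the protocol:
- 24 yoga classes of 90 minutes: about 60 postures, 10 transition and relaxation, and 20 recorded breathing (3.3.2.11).
- Walking sessions of 60 minutes (3.3.2.12).
- Attendance on site for randomization and the week 4, 8 and 12 interventions (3.3.2.11). That makes 3 or 4 in-person sessions, depending on whether the randomization visit includes one.

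Virtual sessions: 24 − 4 = 20, or 24 − 3 = 21.

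Assumption: check-ins total 5, 10 or 15 minutes per walking session. The documents give no length.

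| Check-in total (assumed) | Walking contact, 20–21 sessions | Ratio, yoga counted as 60 min | 70 min | 90 min |
|---|---|---|---|---|
| 5 min | 100–105 min | 12 | 14 | 18 |
| 10 min | 200–210 min | 6 | 7 | 9 |
| 15 min | 300–315 min | 4 | 4.7 | 6 |

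Each ratio is yoga minutes divided by check-in minutes, for example 60/15 = 4 and 90/5 = 18. In person the ratio would be 70/60 ≈ 1.2 or 90/60 = 1.5. Any live step reports during a walk would lower the virtual ratios.

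**2. Can the planned covariates separate contact from arm?**

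Design matrices were built for 35 hypothetical participants per arm.
- *Instructor:* three yoga instructors and two walking monitors, none serving both arms (assumed). Intercept, arm and four indicators give 6 columns with rank 5, so arm is fully aliased.
- *Individual or group session, if it equals arm:* 3 columns, rank 2.
- *Share of individual sessions,* assumed 0–0.05 in yoga and 0.80–0.88 in walking: full rank, but the variance inflation factor for arm is about 485.
- *Group size and sex mix, varying within arm:* 4 columns, rank 4. These do not coincide with arm, but they do not measure contact either.

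The planned primary term is group x time. Entered as main effects only, these covariates leave it estimable and, with complete data, unchanged, so they remove none of the contact difference. Crossed with time, instructor is aliased with group x time. Session format is aliased or nearly so if virtual walking is solitary.

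**3. What a contact-only effect could do (illustration)**

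Take 35 per arm (3.5.2), two-sided alpha 0.05 and a simple comparison of two means. Suppose the only true difference is a contact effect of d standard deviations. The chance of a significant arm difference is Φ(d/√(2/35) − 1.96) + Φ(−d/√(2/35) − 1.96), with √(2/35) = 0.239.

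| d (assumed) | 0 | 0.1 | 0.2 | 0.3 | 0.5 |
|---|---|---|---|---|---|
| Probability | 0.05 | 0.07 | 0.13 | 0.24 | 0.55 |

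These are not type I errors for the package comparison. They are the chances of a result that would be wrongly credited to postures and breathing.

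**The case against.** Several points count against a harsher reading, and most of them stand in part.

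- *Section 4.6.1.17.* A reader might infer that it claims the arms are equivalent. Its sentence says only that no participant straddles the in-person and virtual formats. It is silent on the difference between arms, which makes it incomplete rather than false.
- *Solitary walking.* A reader might infer that virtual walkers have no contact between check-ins. The four step recordings, the option of reporting to the monitor and the simultaneous group slots in 3.3.2.12.1 leave this open. What stands is that the text requires nothing beyond the check-ins and describes no shared call.
- *Small yoga groups.* Planned accrual is 25 randomized per year (3.3.2.2). That gives 25 × 12/52 ≈ 5.8 concurrent participants, about 2.9 per arm. At two sessions each over four weekly slots, this is 2.88 × 2/4 ≈ 1.44 attendees per slot. If attendance is spread at random, e^−1.44 ≈ 24% of yoga attendances would have no other participant. Individual sessions would then also occur in yoga, so session format need not coincide with arm and the inflation factor of 485 would fall. The peer-group advantage would also be smaller. Contact with the instructor would remain unequal.
- *Purpose of the covariates.* They are listed for cohort effects, not contact, and neither document crosses them with time. A reader might infer that the primary contrast is non-estimable, but that would require a model the plan does not specify.
- *Matching.* Matching on contact is stated for Study 2. For this trial, 3.3.2.12 claims a match on physical activity, and 90 versus 60 minutes was unequal by design. Even so, its argument for the shorter session depends on comparable group interaction.

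**Conclusion.** The point holds in this form. As written, virtual delivery probably leaves staff contact and group effect unequal between arms for about 20 to 21 of 24 sessions, and no planned covariate can correct a factor determined by arm. The direction is clear from the text. The size is not: 4- to 18-fold rests on assumed check-ins of 5 to 15 minutes and on no required contact in between.

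A reader might go further and infer that the trial's comparison is invalid. The documents do not support that. Aim 1 compares the yoga intervention with the walking intervention, and randomization protects that comparison of packages as delivered. What is lost is attribution to postures and breathing.

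Nor do all the listed covariates coincide with arm. Instructor does if no one serves both arms. Session format and cohesion largely do if virtual walking is solitary. Group size and sex mix need not.

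**What to change.** 1. In Protocol 3.3.2.12 and 3.3.2.12.1, state that virtual walking runs in the existing simultaneous slots as a shared call, with the walking monitor present throughout as in the in-person design. Log contact minutes and mode for every session in both arms.
2. In Protocol 3.5.1 and SAP D.17, remove instructor, individual or group session, and cohesion as adjusters of the arm comparison. Describe them within each arm, or fit instructor or class as a random effect nested in arm.
3. In Protocol 4.6.1.17, add that the virtual change also alters contact between arms. For participants already treated, word the conclusion as the effect of the whole package, contact included.

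**Cost.** Items 2 and 3 are changes of wording. Item 1 uses slots and a monitor role already in the protocol, although the documents do not show whether one monitor can follow walkers in different places for 60 minutes. Walkers lose some flexibility in timing, and the conclusion becomes narrower. If a shared call proves unworkable, the contact log and the package wording are still needed.

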3.3.2.13. Clinically Significant Abnormalities: If a participant's tests have clinically significant

abnormalities or unexpected findings, they will be told. Specifically, females will be told if they are pregnant. If the serum progesterone level is not less than or equal to 0.03 ng/ml, the participant will be told and possibly asked to repeat the test. If there is a clinically significant finding on the anatomic MRI, the participant will be informed by the study PI, an M.D., within 7 days of receipt of the report by phone or in person. It is McLean's policy to call the listed physician if there is an abnormality found during the MRI reading that requires immediate attention. If the participant gives written permission a copy of the report will be forwarded to the identified physician.

3.3.2.14. Assessment for Suicidality and Safety Plan: Participants are screened weekly for suicidality by use of an Adverse Events sheet that they are required to turn in at the first session of the week, either in-person or virtual. This form may be collected by the Project Manager, or research staff. Due to the addition of virtual interventions, the form can be filed out by research staff over the phone. If there is an indication of increased depression or suicidal ideation, the project manager will inform the research staff or the PI that an assessment of the participant is required. There are also in-person evaluations by research staff at weeks 4, 8, and 12 where participants are assessed for suicidality and increased depressive symptoms. This study excludes individuals with a history of suicidal ideation with intent or a suicide attempt in the last year. This study allows suicidality without intent, which is some individuals is present for years.

Assessment of suicide risk is done using the Columbia Suicide Severity Rating Scale (CSSR-S). The development of suicidality with intent based on the CSSR assessment will result in study withdrawal such that the participant can receive additional conventional treatment. If a member of the research staff concludes that suicidality with intent is present they will develop a safety plan with the participant that can include support by friends or family, the inclusion of their medical treaters, being taken to the VABHCS Mental Health Clinic, where admission to an in patient unit can be arranged. If there is a safety concern after 3:30 when the Mental Health Clinic closes, participants will be referred to Urgent Care or the Lahey Clinic that provides after hours emergency services for the VABHCS. If the participant can be managed safely as an outpatient, arrangement will be made for follow-up treatment. It is noteworthy suicidality decrease in Phase 1 in civilians and no subject were withdrawn from the study for increased symptoms.

3.3.2.15. Potential Problems: Recruitment goals will be assessed every 6 months. If recruitment falls behind schedule, study staff will meet with the staff from the numerous clinic programs at the VABHCS to inform them of this research opportunity. If enrollment in the imaging component is behind due to nicotine use causing more than 10% of exclusions in a 6 month period, the inclusion criteria regarding smoking will be increased to include all subjects, regardless of abstinence.

3.3.2.16. Acquisition of Mood Scales and Psychological Tests: Participants will enter self-report mood and psychological scales onto paper forms. Investigator completed psychological mood and psychological scales will be entered into the REDCap database by research staff. The computers used for storage of mood scales and psychological tests will be VA computers.

3.3.2.17. Acquisition and Analysis of GABA MRS and MRI images: Acquisition and Analysis of GABA MRS and MRI images: All MRS/MRI data will be collected on a Siemens 3T scanner at the McLean Imaging Center (MIC), McLean Hospital, Belmont, MA. High-resolution, 3D T1-weighted anatomical images will be acquired to prescribe the voxel with anatomical precision and reproducibility. Placement algorithms developed in our prior studies will be used for consistent voxel placement, based on anatomic landmarks, in the left thalamus (2x2x3 cm). A single-voxel proton MRS GABA difference-editing technique, MEscher-GArwood Point-Resolved Echo Spectroscopy Sequence – MEGAPRESS, will be used for spectral acquisition, as it permits detection of high-quality GABA spectral data. MEGAPRESS allows for collection of TE 68ms PRESS spectra for the detection of other important metabolites such as creatine, NAA, choline and glutamate. MEGAPRESS is a well-established GABA spectral difference-editing method that isolates the GABA doublet at 3.00 ppm *in vivo*. (78) When used in conjunction with PRESS (point-resolved spectroscopy). Resting state data

has been collected at pre-randomization in Study 4, and now can be collected pre and post the intervention to assess for changes in resting state over the course of the study. A resting-state fMRI scan of 8-10 minutes will complete the one-hour scanning. If time constraints require, the resting-state fMRI scan will not be done. Minor adjustments in the protocol within the safety parameters that do not change the science of the study are allowed.

As discussed with VACO, if there is a problem acquiring scans at the McLean Hospital (e.g. system upgrade) the study can proceed without the imaging component without a protocol deviation.

3.3.2.18. Acquisition and Analysis of PNS Measures: This protocol was used in Study 4. The skin will be cleaned with an alcohol wipe prior to placement of three electrodes at heart level in the left mid-axillary line, above the umbilicus, and under the right clavicle. ECG data will be collected using a GGP Biolog IBI monitor (UFI, Morro Bay, CA) in three consecutive phases: (1) resting, while sitting quietly for 5-minutes; (2) step, a 3-minute challenge using the YMCA Step protocol; and (3) recovery, a 5-minute sitting period. The YMCA Step Test is a standardized test used for 30 years as part of the YMCA Fitness Testing and Assessment Manual.(81) The Official YMCA test consists of stepping up and down on a 12-inch step in time to a 96 per second metronome for a total of 26 step cycles per minute. As in Study 4, the test will be modified to use an 8-inch step to increase subject ease. The step challenge is designed to remove the vagal brake such that RSA decreases and then increases during the recovery period.(82) ECG data will be obtained prior to randomization, and pre- and post-intervention at week 4, week 8, and week 12, and before each MRS scan. The ECG data will be acquired using a Faros Bittum 180 and software approved and installed on VA computers transferred to a VA computer using the 3991xGPP Biolog program (see attached Faros Bittum manual). The data will be blinded and sent to [name] for analysis.

